15.0 Publication Policy

Publication policy, rights, and obligations for this study have been negotiated, detailed, and defined in the study's contractual documents with the clinical site and investigators.

16.0 Clinical Study Administration and Investigators

16.1 Approvals and Agreements

The sponsor, national principal investigator(s), and the principal clinical investigators for each clinical site shall agree to this document and any modifications. A justification for any modifications will be documented. Approval and agreement will be indicated by signing the signature page provided with this document.

16.2 Investigators

To see a complete list of the sponsor, manufacturer, monitor, and data coordinating center along with their contact information, please refer to Appendix A. A complete list of the national principal investigator(s), principal clinical investigators, and coordinating clinical investigators, along with their qualifications and contact information, will be maintained by the data coordinating center. Names and addresses of all clinical sites and other institutions involved in the clinical study (e.g., core labs) will also be maintained by the data coordinating center.

16.3 Insurance

Insurance for the study will be obtained by the sponsor prior to patient enrollment.

17.0 Study Timeline

Table 17.1 projects the study timeline.

Table 17.1. Study timeline

Estimated date of study initiation (at least one site with IRB/EC/REB approval, contract signed, and site training/initiation)	Prior to completion of the second quarter of 2014
Estimated monthly number of study sites with IRB approvals	1
Expected date of initiation of subject enrollment	Prior to completion of the second quarter of 2014
Estimated number of subjects enrolled per month	2 per active site
Estimated date for subject enrollment completion	18-30 months after all sites are eligible to enroll

Expected date to complete follow-up of all study participants	Approximately 24 months after the last patient is enrolled
Expected date for final report submission	3 months after study completion (i.e., after the last patient completes their last follow-up visit)

APPENDIX B

Written Procedures for Monitoring Studies

A. Selection of the monitor.

Designated by the sponsor to oversee the clinical study, the monitor may be an employee of Cook, an employee of a monitoring organization (CRO), or an independent contractor or consultant. The monitor shall be qualified by training and experience to monitor the study in accordance with all applicable regulations and standards for conducting clinical studies.

B. General duties of the monitor.

The monitor must ensure that the study is conducted in accordance with:

1. The signed investigator agreement.
2. The Clinical Investigation Plan (CIP).
3. Any conditions imposed by the IRB/EC/REB or regulatory authority.
4. The requirements of the applicable regulations and standards.

C. Reports by the monitor to the sponsor.

1. Any noncompliance with the items listed above. In the event that the investigator is not complying with the requirements outlined above, it is the sponsor's responsibility to secure compliance.
2. Any adverse events or effects that are potentially reportable to a regulatory authority.

D. Initiating the study.

Prior to initiating any clinical use of the device, the monitor/sponsor representative will participate in a pre-study or initiation visit with each clinical site.

At a minimum, the following items shall be addressed during the site initiation visit:

1. Provide training to investigator on his/her responsibilities per the investigator agreement, applicable laws, regulations and standards; and
2. Provide training to investigator that the IRB/EC/REB approval letter and informed consent/patient information should be on file before initiation of the clinical study.

Additionally, training may be provided to the investigator on:

1. The regulatory status of the device and the requirements for the accountability of same;
 2. The nature of the CIP;
 3. The requirements for an adequate and well-controlled clinical study;
 4. His or her obligation to obtain informed consent in accordance with applicable regulations;
 5. His or her obligation to ensure continuing review of the clinical study by the IRB/EC/REB in accordance with conditions of approval and applicable regulations and to keep the sponsor informed of such IRB/EC/REB approval and subsequent IRB/EC/REB actions concerning the study;
 6. The importance of access to an adequate number of suitable patients to conduct the study;
 7. The importance of adequate facilities for conducting the clinical study; and
 8. The importance of sufficient time from other obligations to carry out the responsibilities to which the investigator is committed by applicable regulations.
- E. During the course of the study, at the direction of the project manager, the monitor should visit the site frequently enough to ensure that:
1. The facilities and research staff used by the investigator continue to be acceptable for purposes of the clinical study;
 2. The applicable version of the CIP and agreements are being followed;
 3. Changes to the CIP, informed consent/patient information have been approved by the IRB/EC/REB and/or reported to the sponsor and the IRB/EC/REB;
 4. Accurate, complete, and current records are being maintained;
 5. Accurate, complete, and timely reports are being made to the sponsor and IRB/EC/REB; and

6. The investigator is carrying out the agreed-upon activities and has not delegated them to other previously unspecified staff.

As appropriate, the following tasks could be performed during periodic visits:

1. Device accountability review;
2. Adverse event review to ensure that events are appropriately reported within the time periods required by the sponsor, CIP, IRB/EC/REB, and applicable regulatory requirements; and
3. Source data verification per the monitoring plan to determine that:
 - a. Informed consent/patient information has been documented in accordance with applicable regulations and expectations of the local IRB/EC/REB;
 - b. The information recorded in the CRFs (paper or electronic) is complete, accurate, and legible;
 - c. There are no omissions in the CRFs of specific data elements, such as the administration to any patient of concomitant test articles or the development of an intercurrent illness;
 - d. Missing visits or examinations are noted; and
 - e. Patients failing to complete the clinical study and the reason for each failure are noted.

F. Records of the monitor.

The monitor shall prepare and maintain records of each initiation visit and each periodic visit, general site contact, or discussion. These will include:

1. Date, name, and address of the investigator, and names of other staff members present at each meeting.
2. A summary of the findings of the visit.
3. A statement of any action taken by the monitor or investigator to correct any deficiencies noted.
4. The monitor shall immediately notify the sponsor of any conditions of noncompliance with the CIP, conditions of IRB/EC/REB or regulatory authority approval, or the applicable regulations.

APPENDIX C

Definitions

Access site complications with clinical sequelae - Arteriovenous fistula, hematoma, or bleeding requiring transfusion (≥ 2 units), hospitalization (either admission or extended stay), or further treatment.

Access site thrombus – Occlusive or nonocclusive thrombus developing at venotomy site after filter insertion or retrieval, documented by ultrasound or other imaging.

Adverse events – Definition may be found in applicable regulations.

Adverse device effects – Definition may be found in applicable regulations.

Clinical fracture – A loss of structural integrity (breakage or separation) of the filter identified by imaging and associated with clinical sequelae and/or requiring intervention.

Clinical migration – Caudal or cranial movement of a filter resulting in surgical or endovascular intervention.

Clinical perforation – Protrusion of filter legs through the wall of the IVC causing hemorrhage or hematoma or touching, impressing, or perforating another organ (e.g., liver, bowel, aorta, psoas muscle, vertebral body, lymph nodes). Acute perforation occurring during placement of the filter is considered a placement problem. Documented using CT.

Deep vein thrombosis (DVT) – Thrombus in the deep veins, usually of the lower extremities or pelvis. Documented by contrast venography, duplex ultrasound, CT, or magnetic resonance (MR) venography. The proximal extent of thrombus should be identified.

Device deficiencies – Definition may be found in applicable regulations.

Filter deformation – Insufficient opening of filter (i.e., filter legs do not adjust themselves to the size of the IVC), collapse of filter, uneven distribution of filter legs, bending of filter, or crossing or entangling of two or more filter legs.

Filter embolization – Post-placement movement of the filter or its components to a distant anatomic site completely out of the target zone (i.e., heart/lungs). Documented by imaging or autopsy.

Filter fracture – Any loss of structural integrity (breakage or separation) of the filter identified by imaging or autopsy. Documented by imaging or at autopsy.

Filter leg interaction with the IVC¹ –

- Grade 0: Normal; filter strut confined entirely within the IVC.
- Grade 1: Filter strut is immediately adjacent to the external aspect of the IVC wall (likely reflecting tenting of the IVC wall).
- Grade 2: Filter strut is entirely outside of the IVC lumen and within the retroperitoneum as evidenced by a “halo” of retroperitoneal fat around axially viewed strut.
- Grade 3: Filter strut is touching, impressing, or perforating another organ (e.g., liver, bowel, aorta, psoas muscle, vertebral body, lymph nodes).

Filter migration – Change in filter position compared to its deployed position (cranial or caudal). Migration will be classified as significant (i.e., ≥ 20 mm) or insignificant (i.e., < 20 mm). Documented by plain radiograph, CT, or venography.

Filter tilt – Angle of the longitudinal axis of the filter with respect to the longitudinal IVC axis. Tilt will be classified as significant (i.e., $\geq 16^\circ$ relative to the IVC longitudinal axis) or insignificant (i.e., $< 16^\circ$ relative to the IVC longitudinal axis). A filter is considered free of tilt if it appears centered in the IVC. Documented by plain radiograph or venography.

¹ Oh JC, Trerotola SO, Dagli M, Shlansky-Goldberg RD, Soulen MC, Itkin M, et al. Removal of retrievable inferior vena cava filters with computed tomography findings indicating tenting or penetration of the inferior vena cava wall. *J Vasc Interv Radiol.* 2011;22:70-74.

IVC thrombotic occlusion – Presence of an occluding thrombus in the IVC occurring after filter placement. Documented by ultrasound, CT, MR, venography, or autopsy. Methods of diagnosis should be noted, along with extent of thrombus. May be symptomatic or asymptomatic.

Major adverse events – Events of clinical perforation, clinical migration, clinical fracture, embolization of the filter or filter fragments to the heart or lungs, IVC thrombotic occlusion, new symptomatic DVT while a filter is indwelling, access site complications with clinical sequelae, and procedure-/device-related death.

Premature release of filter – The filter is released from the deployment system before the physician intended.

Procedure-/device-related death – Death directly attributable to the filter or filter placement or retrieval procedure itself, documented by clinical findings, imaging, or autopsy, or as adjudicated by a Clinical Events Committee.

Pulmonary embolism (PE) – Emboli to lungs via the pulmonary artery, which can arise from deep venous thrombosis in the lower extremities or pelvis. Documented using pulmonary arteriography, cross-sectional imaging, or significant change in ventilation/perfusion lung scan, or at autopsy. PE will be categorized by type.²

Pulmonary embolism (PE), massive – Acute PE with sustained hypotension (systolic blood pressure < 90 mmHg for at least 15 minutes or requiring inotropic support, not due to a cause other than PE, such as arrhythmia, hypovolemia, sepsis, or left ventricular [LV] dysfunction), pulselessness, or persistent profound bradycardia (heart rate < 40 bpm with signs or symptoms of shock).

² Jaff MR, McMurtry MS, Archer SL, Cushman M, Goldenberg N, Goldhaber SZ, et al. Management of massive and submassive pulmonary embolism, iliofemoral deep vein thrombosis, and chronic thromboembolic pulmonary hypertension: A scientific statement from the American Heart Association. *Circulation*. 2011;123:1788-1830.

Pulmonary embolism (PE), submassive – Acute PE without systemic hypotension (systolic blood pressure \geq 90 mmHg) but with either right ventricular (RV) dysfunction or myocardial necrosis, where:

RV dysfunction is defined as the presence of at least 1 of the following:

- RV dilation (apical 4-chamber RV diameter divided by LV diameter $>$ 0.9) or RV systolic dysfunction on echocardiography;
- RV dilation (4-chamber RV diameter divided by LV diameter $>$ 0.9) on CT;
- Elevation of BNP ($>$ 90 pg/mL);
- Elevation of N-terminal pro-BNP ($>$ 500 pg/mL); or
- Electrocardiographic changes (new complete or incomplete right bundle-branch block, anteroseptal ST elevation or depression, or anteroseptal T-wave inversion).

Myocardial necrosis is defined as either of the following:

- Elevation of troponin I ($>$ 0.4 ng/mL) or
- Elevation of troponin T ($>$ 0.1 ng/mL).

Pulmonary embolism (PE), low-risk – Acute PE and the absence of the clinical markers of adverse prognosis that define massive or submassive PE.

Serious adverse events – Definition may be found in applicable regulations.

Serious adverse device effects – Definition may be found in applicable regulations.

Significant trapped thrombus in filter – Thrombus filling $>$ 25% of the filter.

Technical placement success – Deployment of filter in a location suitable to provide sufficient mechanical protection against PE with no filter deformation, fracture, premature release, or clinical migration.

Technical retrieval success – Endovascular retrieval of complete filter.

Unanticipated serious adverse device effects – Definition may be found in applicable regulations.

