As with any medical implant, IVC filters are associated with a range of potential adverse events; these events are clearly outlined in Cook's IFUs for its IVC filters. Recent clinical practice guidelines report the incidence of adverse events for IVC filters in general to be as follows:^{7,8}

Table 4.1. Incidence of adverse events for IVC filters as a class

Adverse Event	Reported Rate
IVC penetration	0-41%
Clinically-significant penetration	0.4%
Filter migration	0-18%
Filter fracture	2-10%
Recurrent PE	0.5-6%
Access site thrombus	0-25%
IVC occlusion	2-30%
Insertion problems	5-23%

These event rates are derived from events reported in the clinical literature, and are based on studies for various types of IVC filters and with a wide range of sample sizes (which directly impacts the reported event rates). Moreover, definitions for the events vary among publications; in particular, they include both those that are clinically-significant (i.e., those associated with patient symptoms and/or requiring an intervention) and those without clinical consequences. Therefore, the data should be interpreted carefully.

In 2010, FDA issued a public notice in which it expressed concerns related specifically to the number of adverse event reports for filter migration, filter embolization, filter fracture, and perforation of the IVC;⁴ notably, event rates cannot be deduced from the FDA database of reported events. In light of these concerns, FDA recommended that filter retrieval be considered as soon as the mechanical protection against PE is no longer warranted. FDA's recommendation is consistent with literature reports which suggest that patients may be at increased risk of adverse events when filters are left indwelling for extended periods of time; despite the fact that most filters are retrievable, a large percentage are left in place permanently. Several publications have documented the fact that dedicated patient follow-up, with recurring assessment for continued risk of PE, results in increased rates of filter retrieval.⁴⁴⁻⁴⁷ These same authors postulate that increased filter retrieval rates may correlate to reduced incidence of filter complications. This hypothesis has yet to be verified in clinical studies, but some filter practices (both filter placement decisions and clinical follow-up practices) have changed in light of these safety concerns.

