Filter perforation with clinical sequelae	0%
DVT	0.41%
Embolization	0%
Fracture	0.14%
Migration	0.28%

Conclusion

Many clinical studies have been conducted on IVC filters, including Cook's studies of its Günther Tulip[®] and Celect[®] filters; Cook's study results support the safety and effectiveness of its filters. In light of FDA's ongoing concerns regarding the use, performance, and safety of IVC filters, this study is intended to collect additional safety and effectiveness data on Cook's IVC filters (i.e., the Günther Tulip[®] and Celect[®] filters) in patients in need of temporary or permanent IVC filter placement for prevention of PE. The study population and endpoints of interest are similar to those investigated in Cook's previous IVC filter studies, to those of interest in the literature, and to those of interest to FDA⁴ and several physician society groups.⁴⁹ Results of this study will be provided to FDA and may be used to support expanded indications for Cook's IVC filters, and may also be compared to safety and effectiveness results associated with implantation of other filter types to the extent that this protocol is consistent with the PRESERVE study.

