8.1.2 Primary Safety Hypothesis

The primary safety endpoint is the rate of 12-month freedom from major adverse events. Major adverse events are defined as: clinical perforation, clinical migration, clinical fracture, embolization of the filter or filter fragments to the heart or lungs, IVC thrombotic occlusion, new symptomatic DVT while a filter is indwelling, access site complications with clinical sequelae, and procedure-/device-related death. The analysis requires that the performance goal of 80% be met for freedom from major adverse events at 12 months. The performance goal was derived based on what are considered clinically acceptable rates for each complication in the overall population.⁴⁸

The null (H_0) and alternative (H_A) hypotheses are expressed as follows:

$$H_0: S(t) \leq 80\%$$

$$H_a: S(t) > 80\%$$

where:

- t is time through 12 months
- $S(t)$ is the true rate of freedom from major adverse events at time t .

The hypothesis will be assessed using a Z-statistic. The Z-statistic is given by

$$Z = (\hat{S}(t) - 0.8)/SE$$

where:

- $\hat{S}(t)$ = Kaplan-Meier estimate of freedom from major adverse events ($S(t)$) at 12 months
- SE = Standard Error = $\sqrt{V(S(t))}$, where $\hat{V}(\hat{S}(t))$ is the estimate of the variance of the Kaplan-Meier estimate using the methods described by Peto et al.⁵⁰

The performance goal will be said to have been met provided the null hypothesis is rejected in favor of the alternative if $\hat{S}(t) - 0.8 > Z_{\alpha}SE$, for $\alpha = 0.025$. The hypothesis will be tested only for patients receiving Celect[®] filters.

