8.3 Sample Size

The study is designed to enroll 320 patients in the Celect[®] filter stratum (to evaluate the safety and effectiveness hypotheses) and up to 150 patients in the Günther Tulip[®] filter stratum at up to 40 sites globally. At least half of the study patients in the Celect[®] filter stratum will be enrolled at US sites.

For the primary effectiveness endpoint, based on what are considered clinically acceptable rates for technical placement success and new symptomatic PE in the overall

population, a performance goal of the rate of technical placement success and 12-month freedom from new symptomatic PE while a filter is indwelling was established to be 90%.⁴⁸ Additionally, based on the data from previous Cook sponsored studies (as summarized in Section 4.0), the rate of technical placement success and 12-month freedom from new symptomatic PE while a filter was indwelling was estimated to be 98.4% for the Celect[®] filter stratum. A sample size of 70 patients will be required to assess the primary effectiveness hypothesis for the Celect[®] filter stratum, with a one-sided exact binomial test, at a type I error rate of 0.025, and a power of 0.9. The calculation was performed with the SAS UnifyPow macro.

For the primary safety endpoint, based on what are considered clinically acceptable rates for each complication in the overall population, a performance goal of the rate of 12-month freedom from major adverse events was established to be 80%.⁴⁸ Based on the data from previous Cook-sponsored studies (as summarized in Section 4.0), the rate of 12-month freedom from major adverse events was estimated to be 92.2% for the Celect[®] filter stratum. A sample size of 88 patients will be required to assess the primary safety hypothesis for the Celect[®] filter stratum, with a one-sided exact binomial test, at a type I error rate of 0.025, and a power of 0.9. The calculation was performed with the SAS UnifyPow macro.

Based on sample size calculations, a minimum of 88 patients in the Celect[®] filter stratum will be required to evaluate the safety and effectiveness endpoints. Cook intends to enroll 320 patients in the Celect[®] filter stratum; this sample size allows for an attrition rate of 72% (i.e., 60% of filters to be retrieved prior to 12 months and an additional 12% of patients who may die, withdraw, or become lost to follow-up). The study may also enroll up to 150 patients in the Günther Tulip[®] filter stratum.

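### The 0.9 safety power in Section 8.3 belongs to a narrower perforation event than the primary safety endpoint counts; the net error in power is unknown and should be worked out

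*Combined protocol and SAP*

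**What the plan says.** **The tested endpoint.** Sections 6.3.2 and 8.1.2 make clinical perforation a component of the major adverse event (MAE) composite. Appendix C defines it as leg protrusion through the caval wall "causing hemorrhage or hematoma or touching, impressing, or perforating another organ", documented by CT. The organ-contact limb repeats the imaging grade in the same appendix: "Grade 3: Filter strut is touching, impressing, or perforating another organ". Clinical fracture needs sequelae and/or an intervention, and clinical migration needs an intervention. Clinical perforation needs neither. Section 7.7 schedules a contrast CT at 365 ± 30 days specifically to look at leg interaction with the cava.

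**The planning rate.** Section 8.3 relies on the earlier sponsor studies described in Section 4.0: "the rate of 12-month freedom from major adverse events was estimated to be 92.2" per cent. It sizes the Celect stratum at 88 patients "with a one-sided exact binomial test, at a type I error rate of 0.025, and a power of 0.9". In Section 4.0 the only perforation item, both in Table 4.3 and in the text on overall event rates, is "Filter perforation with clinical sequelae", at 0%. No rate of organ contact on CT is given for those studies.

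**The test.** Section 8.1.2: "The analysis requires that the performance goal of 80% be met". The comparison is a Z-test on the 12-month Kaplan-Meier estimate, not the exact binomial test used for sizing.

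**The concern.** A planning rate supports a power statement only if it counts the same events as the endpoint. Here one component was defined by clinical sequelae in the source data and by CT appearance in the trial, and the trial looks for that appearance systematically at the visit that fixes the primary time point. The source data had no such item, so silent contact contributes nothing to the 92.2%.

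Two things are at stake. The 0.9 in Section 8.3 cannot be read as the chance of meeting the 80% goal for the endpoint as written. And if the goal were missed, the plan has no version of the composite that uses the planning definition of perforation, so the result could not be set like for like beside the rates that justified the design.

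**Working it through.** **1. Reproduce the 88.** Inputs (Sections 8.1.2 and 8.3): null 80%, alternative 92.2%, one-sided level 0.025, exact binomial. At n = 88, success needs at least 78 event-free patients: P(X ≥ 78 | 0.80) = 0.0238 and P(X ≥ 78 | 0.922) = 0.919. No smaller n reaches 0.90. Attrition agrees: 320 × (1 − 0.72) = 89.6. The arithmetic is sound for 80% against 92.2%.

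**2. Add silent contact to the 92.2%.** The rate is an assumption, since the documents give none. Added events are taken as disjoint from those already counted. Power = P(X ≥ 78 | n = 88, 0.922 − g):

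| Added points g | True rate | Exact power, n = 88 |
|---|---|---|
| 0 | 92.2% | 0.919 |
| 1 | 91.2% | 0.850 |
| 2 | 90.2% | 0.758 |
| 3 | 89.2% | 0.649 |
| 5 | 87.2% | 0.419 |

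**3. What the 92.2% seems to contain.** 119/129 = 92.2%, so ten events in the 129-patient Celect study. Section 4.0 gives an overall Celect event rate of 9.3% = 12/129; removing the two PEs leaves ten. The Celect events it lists other than deaths are two PEs, one DVT and one migration without sequelae: 4/129 = 3.1%, eight short of twelve. The eight deaths within 30 days fill the gap, giving 1 DVT + 1 migration + 8 deaths = 10. This is inferred. Section 8.3 does not itemise the figure, and the Section 4.0 list of outcomes behind the 9.3% does not name death.

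**4. The offset.** Under Appendix C, migration is an MAE only if it leads to an intervention, and death only if directly attributable to the filter or a procedure. If only the DVT qualifies, the base rate is 128/129 = 99.2%, a gain of 9/129 = 7.0 points. Exact power at n = 88 from that base is 0.987 with 5 points of silent contact, 0.921 with 7, 0.852 with 8 and 0.651 with 10. If some early deaths were attributable, the offset is smaller.

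**5. The planned test.** The n = 88 figures use only patients who reach 12 months; Kaplan-Meier also uses censored patients. A Wald approximation at n = 88, starting from 92.2%, gives 0.989 with no added contact, 0.896 with 2 points and 0.525 with 5. I also simulated the Kaplan-Meier Z-test: 320 patients, 60% retrieved and 12% otherwise lost during the first year, other MAEs 1%, CT dates uniform over days 335 to 395, contact dated at the CT. All but the enrolment and attrition figures are assumptions. Ranges cover repeat simulations:

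| Silent contact | Read at day 395 | Read at day 365 |
|---|---|---|
| 8% | 0.89–0.92 | 1.00 |
| 10% | 0.73–0.75 | 0.996 |
| 12% | 0.50–0.57 | 0.99 |
| 15% | 0.22–0.24 | 0.94–0.95 |

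The columns differ because about half the CT findings are dated after day 365. The plan tests the estimate at 12 months and gives no rule for dating a CT finding made within the visit window.

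**The case against.** The strongest reply is that the mismatch may cost nothing. The 92.2% appears to overcount other components, so about 7 points of silent contact could be absorbed with exact power still at 0.92. In the simulation with 1% other MAEs, power falls clearly below 0.9 only at about 10% contact or more, and only with the later reading. The broader definition is also conservative: it makes the 80% goal harder to meet and does not inflate the type I error. All of this stands. It limits the conclusion about size and direction, but it does not make the planning rate match the endpoint, and the offset is itself a reason to itemise the 92.2%.

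A reader might take the spread in Table 4.1, 0–41% for IVC penetration against 0.4% for "Clinically-significant penetration", as showing how far the definition can move this component, or conclude that perforation is the likeliest source of events. The documents support neither. The 0–41% covers any penetration across filter types, and Section 4.0 itself cautions that definitions vary. It is not an organ-contact rate and not specific to Celect.

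Nor is it right that nothing planned would reveal the cause of a failure. Section 6.3.3 reports clinical perforation and leg interaction separately by stratum, and adds a secondary composite that includes Grade 2 or 3 interaction. A failure driven by perforation would show. What is missing is the primary composite recalculated with perforation limited to sequelae or intervention.

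**Conclusion.** The mismatch is established from the text: the 0.9 power is stated for a composite whose perforation item is narrower than the one tested. The size and direction of the resulting error are not established. Taken alone, one point of silent contact moves exact power at 88 patients from 0.92 to 0.85, and five points to 0.42. The inferred make-up of the 92.2% would offset up to about seven points. The planned Kaplan-Meier test can give high or low power at the same contact rate, depending on whether it is read at day 365 or day 395.

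It is tempting to conclude that the trial is underpowered for safety. The documents do not support that: they give no organ-contact rate, and the offset works the other way. The conclusion is that the stated power cannot be relied on for this endpoint until it is recalculated. It rests on the Appendix C wording and the Section 4.0 items. The power figures rest on assumed contact rates, on disjoint events and, for the offset, on the reconstruction from 129 patients.

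**What to change.** Leave the primary definition, the 80% goal and the enrolment as they are.

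- In Section 8.3, itemise the 92.2% event by event under the Appendix C MAE definition.
- State an assumed rate of organ contact on CT, labelled as an assumption. Give power for the planned Kaplan-Meier test over a range, for example 0–15%.
- Say how findings on a CT taken at 365 ± 30 days are dated and counted in the 12-month estimate.
- Pre-specify one supportive analysis of the primary safety composite in which perforation counts only with clinical sequelae or an intervention, reported beside the primary result.

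The cost is revised power text, possibly with a less favourable figure, and one extra analysis of data already collected. Making the change before results are known keeps the supportive analysis from looking post hoc.
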